Pneumonitis has been observed in patients receiving trametinib in combination with dabrafenib. To reduce the risk of pneumonitis, patients will be monitored closely for symptoms, evaluated with imaging and functional tests when appropriate.

	CTCAE Grade
Grade 1	
Grade 2	
Grade 3	
Grade 4	

p. Dose Modification for **Liver Chemistry Changes**

Dabrafenib or Dabrafenib-Trametinib Dose Modification for Liver Chemistry Changes

Dabrateriib of Babrateriib Traffictii	no Dose Modification for Liver Chemistry Changes
Event	Treatment modifications and assessment/monitoring
ALT ≥3x ULN but <5x ULN and TB <2x ULN, without symptoms considered related to liver injury or hypersensitivity and who can be monitored weekly for 4 weeks	 May continue study treatment. Report as SAE if CTEP-AERS reporting criteria is met. If liver chemistry stopping criteria are met any time, proceed as described below.
	MONITORING: Repeat LFT (ALT, AST, ALK, bilirubin) until they return to normal/baseline or stabilise (LFT may be every 2 weeks after 4 weeks if ALT <3x ULN and TB <2 ULN).
 Criteria for discontinuing study drug: When any of the liver stopping criteria below is met, discontinue trametinib and dabrafenib. 1. ALT ≥3xULN and bilirubin ≥2x ULN or >35% direct bilirubin^{1, 2} 2. ALT ≥ 3xULN and INR >1.5, if INR measured² (INR threshold does not apply if subject is on anticoagulant) 3. ALT ≥5x ULN 4. ALT ≥3x ULN persists for ≥4 weeks 	 Immediately discontinue study treatment. Do not restart/rechallenge unless approved by Study Chair. Report as SAE if: 1) CTEP-AERS reporting criteria are met, or 2) patients meet criteria 1-2. Perform liver event ASSESSMENT AND WORKUP (see below). Monitor the subject until liver chemistries resolve, stabilize, or return to baseline (see MONITORING below). If applicable, provide details on required follow up assessments (e.g., follow up for overall survival or disease recurrence or progression). MONITORING: In patients stopping for criteria 1-2 (with abnormal TB

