5. ALT ≥3x ULN and cannot be monitored weekly for 4 weeks 6. ALT ≥3x ULN associated with symptoms³ (new or worsening) believed to be related to liver injury or hypersensitivity	 In patients stopping for criteria 1-2 (with abnormal TB and INR, indicating potentially more significant liver toxicities): Repeat liver chemistries (ALT, AST, ALK, bilirubin) and perform liver event follow-up assessments within 24 hours. Monitor subjects twice weekly until LFT return to normal/baseline or stabilize. A specialist or hepatology consultation is recommended. In patients stopping for criteria 2-6: Repeat LFT and perform liver event follow up assessments within 24-72 hours Monitor subjects weekly until LFTs return to normal/baseline or stabilize. ASSESSMENT and WORKUP: Viral hepatitis serology.⁴ If possible, obtain blood sample for PK analysis.⁵ Serum CPK and LDH. Fractionate bilirubin, if total bilirubin ≥2x ULN.

Event	Treatment modifications and assessment/monitoring
(Contd.)	 CBC with differential to assess eosinophilia. Record clinical symptoms of liver injury, or hypersensitivity on AE CRF. Record concomitant medications (including acetaminophen, herbal remedies, other over the counter medications). Record alcohol use.
	 Additional work up for patient stopping for criteria 1-2 (with abnormal TB and INR, indicating potentially more significant liver toxicities): Anti-nuclear antibody, anti-smooth muscle antibody, Type 1 anti-liver kidney microsomal antibodies, and quantitative total immunoglobulin G (IgG or gamma globulins).
	 Serum acetaminophen adduct HPLC assay (in subjects with likely acetaminophen use in the preceding). If there is underlying chronic hepatitis B (e.g. positive hepatitis B surface antigen): quantitative hepatitis B DNA and hepatitis delta antibody.⁶ Liver imaging (ultrasound, MRI, CT) and /or liver biopsy.

Footnotes:

- Serum bilirubin fractionation should be performed if testing is available. If serum bilirubin fractionation testing is unavailable, record presence of detectable urinary bilirubin on dipstick, which indicates direct bilirubin elevations and suggesting liver injury.
- All events of ALT ≥3xULN and bilirubin ≥2xULN (>35% direct bilirubin) or ALT ≥3x ULN and INR >1.5 (if INR measured) may indicate severe liver injury (possible "Hy's Law"). INR measurement is not required, and the threshold value stated will not apply to subjects receiving anticoagulants.

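### Liver stopping criterion 1 (Section 8.3p) lets a direct bilirubin fraction above 35% act as a trigger with no total-bilirubin floor, in conflict with its own footnote 2

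*Combined protocol and SAP*

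**What the plan says.** The liver table in Section 8.3p gives six stopping criteria and the instruction "When any of the liver stopping criteria below is met, discontinue trametinib and dabrafenib". Criterion 1 reads "ALT ≥3xULN and bilirubin ≥2x ULN or >35% direct bilirubin". Criterion 2 concerns ALT with a raised INR. Criterion 3 is ALT of at least 5x ULN. Criterion 4 is ALT of at least 3x ULN lasting four weeks or more. Criteria 5 and 6 are ALT of at least 3x ULN in a patient who cannot be monitored weekly, or who has liver or hypersensitivity symptoms.

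Meeting criterion 1 or 2 brings an SAE report, repeat liver chemistry within 24 hours, twice-weekly monitoring and an extended work-up. Treatment may not restart without Study Chair approval.

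Other text in the same table bears on criterion 1:

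- **Footnote 2**, attached to criterion 1: "All events of ALT ≥3xULN and bilirubin ≥2xULN (>35% direct bilirubin" (the bracket closes there). It goes on to say that such events may indicate severe liver injury.
- **Work-up list:** "Fractionate bilirubin, if total bilirubin ≥2x ULN".
- **Footnote 1**, also attached to criterion 1, asks for fractionation where the test is available, with no TB condition. Otherwise it asks for a record of urinary bilirubin.
- **Monitoring heading:** "In patients stopping for criteria 1-2 (with abnormal TB and INR, indicating potentially more significant liver toxicities".
- **Row that lets treatment continue:** "ALT ≥3x ULN but <5x ULN and TB <2x ULN, without symptoms considered related to liver injury", followed by "If liver chemistry stopping criteria are met any time, proceed as described below".

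**The concern.** Criterion 1 and its footnote treat the direct fraction differently. The criterion makes it a second route to a stop. The footnote makes it a description of patients who already have TB of at least 2x ULN. Direct fraction is a ratio, so without a floor it can exceed 35% when TB is entirely normal.

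A site following the criterion literally would take such a patient off both drugs and file an SAE. A site following the footnote would not.

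The trigger also depends on local laboratory practice. The monitoring instruction, "Repeat LFT (ALT, AST, ALK, bilirubin) until they return to normal/baseline or stabilise", names bilirubin only. The study calendars schedule serum bilirubin without a direct fraction, and footnote 1 makes fractionation depend on availability. Two patients with the same ALT and TB could be handled differently because only one laboratory reports the direct part.

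**Working it through.** The plan gives no figure to reproduce, because this is a question of wording. The check applies each reading to set patient profiles.

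**Inputs.** The thresholds come from Section 8.3p: ALT 3x and 5x ULN, TB 2x ULN, direct fraction 35%. The profiles are illustrative. They assume no symptoms, weekly monitoring possible, INR not raised and ALT raised for less than four weeks, so criteria 2 and 4 to 6 do not apply.

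**Readings of criterion 1.**

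- A: ALT ≥3x and (TB ≥2x or direct >35%)
- B: (ALT ≥3x and TB ≥2x) or direct >35%
- C: ALT ≥3x and TB ≥2x (footnote 2 floor, direct fraction descriptive)
- D: ALT ≥3x and TB ≥2x and direct >35% (footnote 2, direct fraction required)

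| ALT (x ULN) | TB (x ULN) | Direct | A | B | C | D |
|---|---|---|---|---|---|---|
| 3.5 | 0.8 | 20% | no | no | no | no |
| 3.5 | 0.8 | 40% | stop | stop | no | no |
| 3.5 | 1.5 | 40% | stop | stop | no | no |
| 3.5 | 2.5 | 20% | stop | stop | stop | no |
| 3.5 | 2.5 | 40% | stop | stop | stop | stop |
| 1.0 | 0.8 | 40% | no | stop | no | no |

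The printed sentence supports A or B. Footnote 2 supports C or D. Both footnote readings have the 2x ULN floor and both printed readings lack it.

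**A case with low TB.** Take ALT 3.5x ULN, TB 0.5x ULN and a direct part of 0.2 in the same units. The direct fraction is 0.2/0.5 = 40%, above 35%, so criterion 1 is met under A and B.

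**Extent on a grid.** Cross ALT (<3x, 3x to <5x, ≥5x) with TB (<2x, ≥2x) and direct fraction (≤35%, >35%): 3 x 2 x 2 = 12 cells. Criterion 3 stops all four cells with ALT ≥5x.

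| Reading | Cells meeting criterion 1 | Cells stopped by criterion 1 or 3 |
|---|---|---|
| A | 6 | 7 |
| B | 8 | 9 |
| C | 4 | 6 |

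Against C, reading A differs on criterion 1 membership in 6 − 4 = 2 cells and on stopping in 7 − 6 = 1 cell (ALT 3x to <5x, TB <2x, direct >35%). Reading B differs in 8 − 4 = 4 and 9 − 6 = 3 cells. These counts describe the logic of the rule. They are not frequencies.

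**Whether the cell can be reached.** Section 5.1n admits patients with known liver metastases whose ALT is below 5x the institutional ULN, so a patient can enter with ALT already between 3x and 5x ULN.

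**The case against.** The strongest reply is that a stopping rule may be wider than the Hy's Law description in its footnote. Footnote 2 interprets events and does not itself order a stop. Footnote 1 asks for fractionation without a TB condition, which fits a separate direct-bilirubin limb. Over-stopping is also the cautious error, and the Study Chair can approve a restart. This stands in part: the documents do not settle what was intended. It does not remove the difference between the criterion and its footnote, nor does it explain a trigger with no TB floor when the work-up calls for fractionation only at TB of at least 2x ULN.

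Two further points for the plan are right:

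- A reader might infer that the row allowing treatment to continue contradicts criterion 1, or proves that a TB floor was meant. It does neither. The row defers expressly to the stopping criteria and overlaps criteria 2 and 4 in the same way, so the order of precedence is clear.
- A reader might take the monitoring heading as confirming the 2x ULN threshold. It speaks only of abnormal TB and INR and gives no multiple. It is also loose, since criterion 1 needs no INR and criterion 2 needs no TB. It is weak support.

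The urinary bilirubin record in footnote 1 partly fills the gap where fractionation is unavailable, but a dipstick result is not among the stopping criteria.

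**Conclusion.** Criterion 1 is wrong as written, in that it does not agree with its own footnote on whether a direct fraction above 35% needs TB of at least 2x ULN. The conclusion rests on footnote 2, with the work-up line as secondary support that footnote 1 weakens.

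The severity is minor. Under reading A, the stop decision changes only for patients with ALT 3x to <5x ULN, TB <2x ULN and direct fraction above 35%. Criteria 4 to 6 narrow that group further. Reading B reaches further, to patients with ALT below 3x ULN. Patients with ALT of at least 3x, TB of at least 2x and direct fraction at or below 35% stop under the printed text and under the fix below.

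A reader might infer that the defect affects the trial's results or that a known share of patients would be wrongly stopped. The documents support neither. The DLT definitions in Sections 7.3c and 7.4c do not use this criterion, the response endpoint and two-stage design are unaffected, and nothing in the documents says how often the profile occurs.

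**What to change.** Reword criterion 1 as: *ALT ≥3x ULN and total bilirubin ≥2x ULN (fractionate if available; do not delay stopping for the result)*. Keep the direct fraction above 35% only as the Hy's Law descriptor in footnote 2, and leave the urinary bilirubin record in footnote 1 as it is. The SAE trigger needs no edit because it refers to criteria 1 and 2 by number.

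The clinical team should confirm the intent first. If the direct fraction was meant as a separate trigger, keep it, state the ALT and TB levels at which it applies, and align footnote 2 and the fractionation instruction.

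The main fix costs one sentence and no extra tests. Its price in protection is that a patient with direct fraction above 35% and TB below 2x ULN no longer stops on that alone. Such a patient stays under weekly monitoring and criteria 2 to 6.

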8.4 Dose Modifications for GSK2141795

a. GSK2141795 Dose Modification for Hypo- or Hyperglycemia

Management and Dos	e Modification Guidelines for	Hypo- or Hyperglycemia					
Criteria	Management Guidelines	Study Drug Modification					
	oses, refer to mild, moderate and rting use NCI-CTCAE version 4						
Mild Fasting blood glucose > 150mg/dL	Monitor fasting and preprandial glucose.	Continue study drug					
Moderate to Severe Fasting blood glucose <70 mg/dL OR any blood glucose > 250mg/dL	If a blood glucose >250 mg/dL, monitor for ketoacidosis as clinically indicated. When managing hyperglycemia associated with GSK2141795, be aware that the action of insulin or other antihyperglycemic agents (e.g., sulfonylureas, biguanides, etc.) may be substantially blocked by the study agent. However the action of antihyperglycemic agents would be restored as GSK2141795 is cleared. The patient should be observed closely for rebound hypoglycaemia as GSK2141795 is held/or discontinued. Intravenous insulin treatment is recommended.	Hold GSK2141795 and notifyinvestigator immediately. Continue dabrafenib and trametinib. The investigator should discuss intervention and possible resumption of GSK2141795 with the Study Chair.					

8.6 Adverse Event Reporting

Toxicities (including suspected reactions) that meet the expedited reporting criteria as outlined in Section 16.1 of the protocol must be reported to the Operations Office, Study Chair and NCI via CTEP-AERS, and to the IRB per local IRB requirements.

9.0 STUDY CALENDAR

9.1 Study Calendar – Phase I D+G Portion

J. 1	olday Galei		Сус				Сус	ole 2			Cycle	e 3 + β		Follow-Up Prior to Progression	At Time of Progression	Post- Progression Follow-Up Ψ
REQUIRED STUDIES	PRE- STUDY	Wk	Wk	Wk	Wk	Wk	Wk	Wk	Wk	Wk	Wk	Wk	Wk			
		1	2	3	4	5	6	7	8	9	10	11	12			
PHYSICAL																
H & P	Х	Х		Х		Х		Х		Х				Х	Χ	Х
Wt & PS	×	Х		Х		Х		Х		Х						Х
Baseline Abnormality Assessment	Х															
Tox Notation		Х		Х		Х		Х		Х				X≠	X≠	X≠
Eye Exam√√	Х															
Derm Exam**	X													X**	X**	X**
Disease Assessment ¥	Х									Х				X	Χ	
Review Intake Calendar						X				X						
LAB ∏																
CBC/ Diff/PLT /Hg	×	X		Х		X		Х		Х						X
Serum Bilirubin	Х	Х		Х		Х		Х		Х						Х
AST & ALT	Х	Χ		Χ		Х		Χ		Χ						X
Serum Creat or CrCl	X	X		Х		X		Х		Х						X
Serum Glucose	Х	Х		Х		Х		Х		Х						
Serum albumin	Х	Х		Х		Х		Х		Х					-	
Amylase/Lipase+	Х	Х		Χ		Х		Х		Χ						
PT/INR, PTT Δ	Х															
LDH Ω	Х															
Pregnancy test (women of child bearing potential)	X															

Section 9.1 Study Calendar continues on next page. Click here for footnotes.

9.1 Study Calendar – Phase I D+G Portion (contd.)

			Сус	cle 1			Сус	cle 2			Cycle	: 3 + β		Follow-Up Prior to Progression	At Time of Progression	Post- Progression Follow-Up Ψ
REQUIRED STUDIES	PRE- STUDY	Wk	Wk	Wk	Wk	Wk	Wk	Wk	Wk	Wk	Wk	Wk	Wk			
STODIES	31001	1	2	3	4	5	6	7	8	9	10	11	12			
X-RAYS & SCANS																
Brain CT or MRI	X															X
CT or MRI ¥	Х									Х				X£	Х	
ECHO or MUGA	Х									Χπ				Χπ		
ECG	Х															
SPECIMEN SUBMISSION																
Blood for PK ∞	Х			Х		Х										
Paraffin-Embedded Tissue/Slides (Fresh Frozen Tissue if Available)	х			ХФ											х	
Plasma and buffy Coat ®	Х									Х					Х	
TREATMENT																
Dabrafenib ∑		Х	Х	Х	Х	Х	Х	Х	Х	Х	Х	Х	Х			
GSK2141795 F		Х	Х	Х	Х	Х	Х	Х	Х	Х	Х	Х	Х			

Click here for **footnotes**.

NOTE: Forms are found on the protocol abstract page of the SWOG website (www.swog.org). Forms submission guidelines are found in Section 14.0.

Footnotes:

- ¥ For the first two years after registration, disease assessments must be performed after every two cycles of treatment using the same method as baseline and must be documented on the Follow-Up Tumor Assessment Form (RECIST 1.1). A response must be confirmed by a second determination at least 4 weeks after a complete or partial response has been noted. After two years (measured from time of registration), the frequency of disease assessment, CT, and MRI may be reduced to once every 12 weeks.
- √√ Ophthalmic exam must be performed at baseline. Follow-up exams should be performed as clinically indicated.
- ** Dermatology exams are required every 2 months throughout treatment, and every 2 months through 6 months after discontinuation of dabrafenib or until the start of another anti-neoplastic therapy.
- π On treatment echocardiogram (or MUGA) should be obtained every 2 months for all patients in the Phase I portion.
- ☐ Patients known to be HIV + must not be on antiviral agents and must have CD34 counts ≥ 500 mm³ (see Section 5.1t).
- Δ See Sections 5.1u and 7.2b.
- B Protocol treatment assessments will continue on this schedule until any one of the criteria in Section 7.8 is met.
- £ Once off protocol treatment, disease assessments must be performed every 8 weeks until disease progression. After two years (measured from time of registration), the frequency of disease assessments, CT and MRI may be reduced to once every 12 weeks.
- Ψ After disease progression (see Section 10.2), follow-up for survival status must be performed every 3 months for the first year, then every 6 months for a total of 3 years from the date of registration or death, whichever is first.
- ≠ Assessments should continue until resolution of all acute adverse events. Patients with AEs at progression should be followed at frequencies appropriate for the nature and duration of the events, until the AE has resolved or is deemed irreversible.
- Σ To be taken twice daily.
- To be taken once a day.
- Ω For melanoma patients only.
- Required at baseline and prior to dosing on Days 15 and 29. Three patients treated within the second cohort of the Phase I Portion (D+G) will have more extensive PK sampling at baseline, pre-dose and +1, +2, +4, and +8 hours on Day 15, and pre-dose Day 29.
- Φ Optional biopsy between Day 15-28.
- ® Plasma and buffy coat must be submitted at baseline, before the start of Cycle 3 and at the time of progression.
- + As clinically indicated to evaluate adverse events (i.e., abdominal pain, pancreatitis, etc).

9.2 Study Calendar – Phase I D+T +G Portion

9.2				cle 1			Сус	ele 2			Cycle	e 3 + β	_	Follow-Up Prior to Progression	At Time of Progression	Post- Progression Follow-Up Ψ
REQUIRED STUDIES	PRE- STUDY	Wk	Wk	Wk	Wk	Wk	Wk	Wk	Wk	Wk	Wk	Wk	Wk			
OTOBIEG	01001	1	2	3	4	5	6	7	8	9	10	11	12			
PHYSICAL																
H & P	Х	Х		Х		Х		Χ		Χ				X	X	X
Wt & PS	Х	Х		Χ		Х		Х		Х					X	Х
Baseline Abnormality Assessment	Х															
Tox Notation		Х		Х		Х		Х		Х				X≠	X≠	X≠
Eye Exam√√	Х															
Derm Exam**	Х													X**	X**	X**
Disease Assessment ¥	×									Х				X	X	
Review Intake Calendar						X				X						
LAB ∏																
CBC/ Diff/PLT /Hg	Х	Х		Х		Х		х		Х						Х
Serum Bilirubin	Х	Х		Χ		Х		Χ		Χ						Х
AST & ALT	Х	Х		Х		Х		Х		Х						Х
Serum Creat or CrCl	Х	Х		Х		Х		Х		Х						Х
Serum Glucose	Х	Х		Х		Х		Χ		Χ						
Serum albumin	Х	Х		Х		Х		Х		Х						
Amylase/ Lipase +	Х	Х		Х		Х		Х		Х						
PT/INR, PTT Δ	Х															
$LDH\Omega$	Х															
Pregnancy test (women of child bearing potential)	x	4:														

Section 9.2 Study Calendar continues on next page. Click here for footnotes.

9.2 Study Calendar – Phase I D+T +G Portion (contd.)

		Cycle 1					Сус	ele 2			Cycle	: 3 + β		Follow-Up Prior to Progression	At Time of Progression	Post- Progression Follow-Up Ψ
REQUIRED STUDIES	PRE- STUDY	Wk 1	Wk 2	Wk 3	Wk 4	Wk 5	Wk 6	Wk 7	Wk 8	Wk 9	Wk 10	Wk 11	Wk 12			
X-RAYS & SCANS				J		J	-	-	J	J						
Brain CT or MRI	×															X
CT or MRI ¥	Х									Х				X£	Х	
ECHO or MUGA	Х									Χπ				Χπ		
ECG	Х															
SPECIMEN SUBMISSION																
Blood for PK ∞	Х			Х		Х										
Paraffin- Embedded Tissue/Slides (Fresh Frozen Tissue if Available)	Х			ХФ											×	
Plasma and Buffy Coat ®	Х									Х					Х	
TREATMENT																
Dabrafenib ∑		Х	Х	Х	Х	Х	Χ	Х	Х	Х	Х	Х	Х			
Trametinib □		Х	Χ	Χ	Χ	Χ	Χ	Χ	Χ	Х	Χ	Χ	Х			
GSK2141795 -		Χ	Х	Χ	Х	Х	Χ	Χ	Χ	Х	Χ	Χ	Χ			

Click here for footnotes.

NOTE: Forms are found on the protocol abstract page of the SWOG website (www.swog.org). Forms submission guidelines are found in Section 14.0.

Footnotes:

- ¥ For the first two years after registration, disease assessments must be performed after every two cycles of treatment using the same method as baseline and must be documented on the Follow-Up Tumor Assessment Form (RECIST 1.1). A response must be confirmed by a second determination at least 4 weeks after a complete or partial response has been noted. After two years (measured from time of registration), the frequency of disease assessments, CT and MRI may be reduced to once every 12 weeks.
- √√ Ophthalmic exam must be performed at baseline. Follow-up exams as clinically indicated.
- ** Dermatology exams are required every 2 months throughout treatment, and every 2 months through 6 months after discontinuation of dabrafenib or until the start of another anti-neoplastic therapy.
- π On treatment echocardiogram should be obtained every 2 months for all patients in the Phase I portion.
- ☐ Patients known to be HIV + must not be on antiviral agents and must have CD34 counts ≥ 500 mm³ (see Section 5.1t).
- Δ See Sections 5.1u and 7.2b.
- B Protocol treatment assessments will continue on this schedule until any one of the criteria in Section 7.8 is met.
- £ Once off protocol treatment, disease assessments must be performed every 8 weeks until disease progression. After two years (measured from time of registration), the frequency of disease assessments, CT and MRI may be reduced to once every 12 weeks.
- Ψ After disease progression (see Section 10.2), follow-up for survival status must be performed every 3 months for the first year, then every 6 months for a total of 3 years from the date of registration or death, whichever is first.
- ≠ Assessments should continue until resolution of all acute adverse events. Patients with AEs at progression should be followed at frequencies appropriate for the nature and duration of the events, until the AE has resolved or is deemed irreversible.
- Σ To be taken twice daily.
- To be taken once a day.
- Ω For melanoma patients only.
- ∝ Required at baseline and prior to dosing on Days 15 and 29. Three patients treated within the second cohort of the Phase I Portion (D+G) will have more extensive PK sampling at baseline, pre-dose and +1, +2, +4, and +8 hours on Day 15, and pre-dose Day 29.
- Φ Optional biopsy between Day 15-28.
- ® Plasma and buffy coat be submitted at baseline, before the start of Cycle 3 and at the time of progression.
- + As clinically indicated to evaluate adverse events (i.e., abdominal pain, pancreatitis, etc).

9.3 Study Calendar – Phase II D+T+G

	ady Galerie		Cycl				Сус	ele 2			Cycle	3 + β		Follow-Up Prior to Progression	At Time of Progression	Post- Progression Follow Up Ψ
REQUIRED STUDIES	PRE- STUDY	Wk 1	Wk 2	Wk 3	Wk 4	Wk 5	Wk 6	Wk 7	Wk 8	Wk 9	Wk 10	Wk 11	Wk 12			
PHYSICAL																
H&P	Х	Х				Х				Х				X	Х	Х
Wt & PS	Х	Х				Х				Х						Х
Baseline Abnormality Assessment	Х															
Tox Notation		Х				Χ				Χ				X≠	X≠	X≠
Disease Assessment ¥	Х									Х				X£	X	
Eye Exam √√	Х															
Dermatology Exam**	X													X**	X**	X**
Review Intake Cal						Х				Х						
LAB ∏																
CBC/Diff/PLT/Hg	Х	Х				Х				Х						Х
Serum Bili	Х	Х				Х				Х						Х
AST & ALT	Х	Х				Х				Χ						Х
Serum Cr or CrCl	Х	Х				Х				Х						Х
Serum Glucose	Х					Χ				Х						
Serum Albumin	Х	Х				Х				Х						
Amylase /Lipase +	Х					Х				Х						
PT/INR, PTT Δ	Х					Х				Х						
LDH	Х															
Pregnancy test (women of child bearing potential)	X															

Section 9.3 Study Calendar continues on next page. Click here for footnotes.

